2.2.10 Interim Analyses

An interim analysis is planned to assess primary efficacy endpoint futility and to adjust sample size; EASI will also be evaluated to judge any futility decision. The sample size may be increased at the interim analysis (conducted after n=150 complete Week 8/Exit) to update primary efficacy endpoint assumptions and to achieve at least 80% power and two-sided 5% Type I error.

2.2.11 Randomization/Unblinding

2.2.11.1 Randomization Methodology

At least 300 patients will be randomized to the three blinded treatment groups in a 1:1:1 ratio as follows:

- Treatment group A: 1g DS107 (2 DS107 capsules and 2 placebo capsules) administered once-daily for 8 weeks

- Treatment group B: 2g DS107 capsules (4 DS107 capsules) administered once-daily for 8 weeks
- Treatment group C: Placebo capsules (4 placebo capsules) orally administered once-daily for 8 weeks

A randomization list, permuted blocks and stratified by site was generated by HMD Clinical ([name]). The randomization schedule with study drug assignments was generated prior to the start of the study and will be known only to the individuals responsible for labelling the study drug, the statisticians generating the schedule and the IWRS team responsible for implementing the schedule. The IWRS will assign a medication kit number to each patient and the contents will be based on the randomization code.

2.2.11.2 Unblinding

All study site personnel, as well as the personnel involved in the monitoring or conduct of the study, will be blinded to the individual patient treatment assignments. Randomisation details will be kept strictly confidential, accessible only in an emergency to authorized persons, until the time of formal unblinding. The blinded code for the trial will be broken only after all patient data has been recorded and verified and the database locked.

Emergency unblinding will be carried out through the IWRS system with relevant site personnel and pharmacovigilance monitors provided with the required system access to carry out un-blinding.

Any unblinding (and reason for unblinding) prior to database lock will be reported in the final CSR.

2.2.12 Efficacy Analyses

Summary statistics by visit will be provided for all efficacy endpoints. For continuous efficacy endpoints, summary statistics will also be provided for change from baseline at each post-baseline visit. Results for the primary and secondary efficacy endpoints will be presented separately for moderate and severe AD as well as combined across moderate and severe AD strata. Models will include a baseline covariate for moderate/severe for all primary and secondary efficacy analyses. Models will be performed for the primary efficacy endpoint for the separate AD strata but not for the secondary efficacy endpoints.

2.2.12.1 Primary Endpoint

The primary efficacy variable will be the proportion of patients achieving an IGA score of 0 (clear) or 1 (almost clear) and a decrease of at least 2 points in IGA from baseline to week 8. This is a binary endpoint.

The primary endpoint will be analyzed using a Generalised Linear Model (PROC GENMOD) with treatment arm, moderate/severe AD, baseline IGA value, visit and DS treatment dose as factors. The primary analysis will be based on the FAS and repeated for the PPS as a supportive analysis.

This analysis will be performed using SAS PROC GENMOD with code similar to the following:

```
proc genmod data=subjresults descending;  
  class trt visit subj AD;  
  model outcome=trt visit trt*visit AD B_IGA /dist=bin;  
  repeated subject=subj/corr=unstr;  
  slice trt*visit / sliceby=visit ilink cl diff;  
run;
```

where fas= Full Analysis Set (FAS), outcome= patients in each treatment arm at week 8 who achieve an IGA score of 0 (clear) or 1 (almost clear) and a decrease of at least 2 points in IGA from baseline. B_IGA is the baseline IGA value.. The dist=bin option of the model statement specifies that the logit transformation will be applied to outcome prior to analysis. The cl option specifies that two-sided 95% confidence intervals will be provided and the ilink option specifies the transformation from the logit scale to the probability scale. The between-treatment effects are determined from the diff option of the slice statement. Results will be presented separately for moderate and severe AD for both the FAS and PPS populations. The model will be used to estimate Week 8 effect.

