The proportion of moderate patients achieving an IGA of 0 (clear) or 1 (almost clear) and a decrease in 2 point in IGA score was significantly greater in the DS107 capsules group (8/29 patients, 28%) compared to placebo group (6/38 patients, 16%) in patients with moderate AD at baseline ($p = 0.036$). Similar efficacy trends were observed in the severe/very severe population where 3 out of 22 patients (13%) treated with DS107 capsules met the Responder criteria compared to 0 out of 13 patients in the Placebo group. Statistical significance could not be achieved due to the low number of patients in each group and lack of primary response in placebo.

The effect of DS107 capsules was consistently higher than placebo for all of the efficacy endpoints evaluated in this study, both investigator scores and patient scores. Pruritus is the most important symptom for patients suffering from AD. It has a significant impact on sleep and quality of life (Hong et al., 2011). Pruritus sensation was significantly decreased from Baseline at Week 4 in patients receiving DS107 compared to patients receiving Placebo. This difference in pruritus was both statistically and clinically significant as shown by a decrease in pruritus of 39.5% for patients randomized to DS107 and of only 10.05% in patients randomized to placebo at week 4.

No deaths or SAEs were observed throughout the course of this study. There were no drug related AE's associated with safety lab results, physical exams or vital signs. AEs were mild to moderate and transient. The most common AEs observed in the DS107 group were gastrointestinal in nature. Overall

the tolerance of DS107 capsules administered over 8 weeks was acceptable in comparison with Placebo and DS107 appears safe and well tolerated.

Topical DS107

Three studies have been completed with DS107 Cream.

A Phase 1 clinical study (DS107E-01) was carried out to investigate the safety and tolerability of topically administered DS107 cream in human volunteers at five dose levels (0.1%, 0.5%, 1%, 2.5% and 5%) applied twice daily for 14 days (with a matched placebo cream).

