7.2 Inclusion Criteria

1. Patients with a clinically confirmed diagnosis of active AD according to Hanifin and Rajka criteria.
2. Patients with moderate to severe AD at baseline as defined by an IGA of minimum 3 at baseline.
3. Patients with an EASI score of ≥ 12 at screening and baseline.
4. Patients with AD covering a minimum 10% of the body surface area at baseline.
5. Patients whose pre-study clinical laboratory findings do not interfere with their participation in the study, in the opinion of the investigator.
6. Patients who are able and willing to stop all current treatments for AD throughout the study (except for allowed emollients).
7. Patients who are on a stable dose of a bland emollient applied BD (twice daily) for at least 7 days prior to baseline.
8. Male or female patients who are aged 18 years and older on the day of signing the informed consent form (ICF).
9. Female patients and male patients with female partners of child bearing potential must use adequate contraception or have a sterilized partner for the duration of the study. Adequate contraception is defined as: systemic hormonal contraceptives, intrauterine device or barrier method of contraception in conjunction with spermicide, or agree to sexual abstinence. Hormonal contraceptives must be on a stable dose for at least one month before baseline.
10. Patients who are able to communicate well with the investigator, to understand and comply with the requirements of the study, and understand and sign the written Informed Consent.

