9 ASSESSMENTS

9.1 Efficacy Assessments

9.1.1 Investigator Global Assessment (IGA)

The clinical severity of AD will be evaluated by the investigator at each visit using the IGA scale (Appendix 3) (Futamura et al. 2016).

The IGA scale awards a score of 0-4 based on a 5-point severity scale from clear to severe disease (0 = clear, 1 = almost clear, 2 = mild disease, 3 = moderate disease, 4 = severe disease). IGA uses clinical characteristics of erythema, infiltration, papulation and oozing/crusting as scoring guidelines for the overall severity assessment. IGA will be assessed at every visit.

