9.1.2 Eczema Area Severity Index (EASI)

EASI (Appendix 4) will be assessed at Screening, Baseline/Visit 2, Week 2/Visit 3, Week 4/Visit 4, Week 6/Visit 5, Week 8/Visit 6/ET and Follow up Week 10/Visit 7. It quantifies the severity of a patient's AD based on both lesion severity and the percent of BSA affected (Hanifin et al. 2001). The EASI is a composite score ranging from 0-72 that takes into account the degree of erythema, induration/papulation, excoriation, and lichenification (each scored from 0 to 3 separately, half points are permitted) for each of four body regions, with adjustment for the percent of BSA involved for each body region and for the proportion of the body region to the whole body.

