2.2.4.4 Subgroup Analyses

Subgroup analyses will be conducted on the primary and secondary endpoints stratifying by severity of atopic dermatitis (moderate or severe), defined as an IGA score of 3=moderate or 4=severe at the Baseline/visit 2 visit, which is consistent with the AD severity used for the entrance criteria in the study. Statistical testing for this subgroup analyses will be limited to the primary efficacy endpoint but summary statistics will be provided for all secondary efficacy endpoints.

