2.2.12.2 Secondary Endpoints

The secondary endpoints are:

- Proportion of patients achieving an IGA score of 0 (clear) or 1 (almost clear) and a decrease of at least 2 points in IGA in treated population compared to placebo population from baseline to Week 2, 4, 6 and change from baseline to subject's last treatment visit. These analyses will be

included in the previous analyses for the primary endpoint for Week 8. A separate model will be performed for the change from baseline to week 10, using the same PROC GENMOD code.

- Proportion of patients achieving a decrease of at least 2 points in IGA in treated population compared to placebo population from baseline to Week 2, 4, 6, 8 and change from baseline to subject's last treatment visit. These analyses will be conducted in the same way as the primary endpoint analysis. A separate model will be performed for the change from baseline to week 10 using the same PROC GENMOD code.

- Change from baseline in Eczema Area and Severity Index (EASI) in treated population compared to placebo population at Weeks 2, 4, 6, 8 and subject's last treatment visit. These will be analyzed using PROC MIXED with treatment arm, moderate/severe AD, baseline IGA value, visit, and DS treatment*visit as factors. A separate model will be performed for the change from baseline to week 10, using the same PROC MIXED code.

The change from baseline in EASI will be analyzed for the FAS with SAS PROC MIXED using code similar to the following, with CFB_EASI and B_EASI representing the change from baseline and the baseline EASI, respectively. Method=ml is the maximum likelihood estimate.

```
proc mixed method =ml data= FAS;  
class trt visit subj AD;  
model CFB_EASI= trt visit visit*trt AD B_EASI /CL;  
repeated subject=subj/corr=unstr;  
lsmeans trt*visit / diff CL;  
run;
```

- Change from baseline in Numeric Rating Scale (NRS) for Pruritus in treated population compared to placebo population at Weeks 2, 4, 6, 8 and subject's last treatment visit. These will be analyzed using PROC MIXED with treatment arm, baseline AD severity, baseline NRS score, visit, and DS treatment*visit interaction as factors. A separate model will be done for the change from baseline to Week 10, using the same PROC MIXED code.

As NRS is a daily assessment, the analysis of NRS will be performed using the daily average at each visit. At each visit, the average of the NRS values since the previous visit will be computed. Missing values for any

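### In the primary IGA model, baseline IGA duplicates the moderate/severe factor; baseline EASI, already collected, should replace it before the interim analysis

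*SAP*

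**What the plan says.** SAP 2.2.12.1 gives the primary code as "model outcome=trt visit trt*visit AD B_IGA /dist=bin", fitted by GEE over visits. AD is a class variable for moderate/severe disease and B_IGA is the baseline IGA value.

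Three other places fix what those two terms can be:
- SAP 2.2.4.4 has severity "defined as an IGA score of 3=moderate or 4=severe at the Baseline/visit 2 visit".
- Protocol 7.2 admits "Patients with moderate to severe AD at baseline as defined by an IGA of minimum 3 at baseline".
- Protocol 9.1.1 caps the scale: "The IGA scale awards a score of 0-4 based on a 5-point severity scale from clear to severe disease".

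EASI is also an entry criterion, "Patients with an EASI score of ≥ 12 at screening and baseline" (protocol 7.2), and is assessed at Visit 2 (protocol 8.2.3 and Appendix 1). It is much finer: "The EASI is a composite score ranging from 0-72" (protocol 9.1.2). The SAP's code for the secondary EASI endpoint already uses it with AD: "model CFB_EASI= trt visit visit*trt AD B_EASI /CL". The prose above that code lists baseline IGA instead.

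Protocol 12.9.2 and the synopsis name treatment arm and baseline IGA for the primary model and do not mention EASI. SAP 2.2.12 also calls for separate primary-endpoint models in moderate and in severe patients.

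**The concern.** The model appears to adjust for two baseline variables but adjusts for one, with two levels. Two patients with IGA 3, one with EASI 13 and one with EASI 40, are given the same expected response apart from treatment and visit. If extent and intensity of disease within an IGA level predict clearing, the analysis leaves out information already in the database, and a chance imbalance in EASI between arms stays uncorrected. The protocol states only 45% power at the Phase 2a rates, so a low-cost gain in precision is worth examining. In the separate moderate and severe models neither AD nor B_IGA varies, so those models have no working baseline covariate.

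**Working it through.** **1. The duplication.** For an eligible patient baseline IGA is 3 or 4. Code AD as 0 for IGA 3 and 1 for IGA 4. Then B_IGA = 3 + AD. The columns {intercept, AD, B_IGA} have rank 2, not 3. Dropping B_IGA leaves the fitted model and the treatment comparison unchanged. (A patient randomised in error with IGA below 3 would have no AD level under SAP 2.2.4.4.)

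**2. The plan's own power.** Protocol 12.3: 21.6% v 11.8%, 100 per arm, two-sided 5%.
- Difference 0.098; mean rate 0.167.
- Null SE = √(2 × 0.167 × 0.833 / 100) = 0.05275.
- Alternative SE = √((0.216 × 0.784 + 0.118 × 0.882) / 100) = 0.05229.
- Power = Φ((0.098 − 1.96 × 0.05275) / 0.05229) = Φ(−0.103) = 45.9%, against 45% stated.

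At the SAP 2.2.9 rates (25% v 10%, 100 per arm) the same formula gives 80.2%.

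**3. Is severity prognostic?** Phase 2a counts, protocol 1.6:
- Moderate: 8/29 active, 6/38 placebo, together 14/67 (20.9%).
- Severe/very severe: 3/22 active ("3 out of 22 patients (13%) treated with DS107 capsules met the Responder criteria"), 0/13 placebo, together 3/35 (8.6%).
- Odds ratio = (3/32)/(14/53) = 0.355; SE of log OR = √(1/3 + 1/32 + 1/14 + 1/53) = 0.674; 95% CI 0.09 to 1.33; Fisher p = 0.16.
- Stratified by arm (Mantel-Haenszel): 0.27, 95% CI 0.07 to 1.12.

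The direction is the same in both arms, but there are only 17 responders and both intervals include 1.

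**4. What adding EASI does to power.** Simulated Week 8 logistic regression, one active arm v placebo, 100 per arm, 10,000 trials per row, marginal response rates held fixed. Assumptions: 34% severe (35/102), severe v moderate OR 0.4, EASI normal within severity level, and the EASI odds ratio per within-level SD shown (the simulation used the reciprocals 1.25, 1.5, 2 and 3, which is equivalent for a symmetric covariate). Compare within rows, since both models were fitted to the same trials; the simulation SE of each power near 45% is about 0.5 points.

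| EASI OR per SD | 21.6% v 11.8%: AD only → AD + EASI | 25% v 10%: AD only → AD + EASI |
|---|---|---|
| 1.0 | 44.9% → 44.9% | 81.5% → 81.4% |
| 0.80 | 46.9% → 46.9% | 82.0% → 82.1% |
| 0.67 | 45.7% → 46.6% | 80.4% → 81.4% |
| 0.50 | 46.8% → 49.5% | 81.4% → 83.7% |
| 0.33 | 45.4% → 51.6% | 81.4% → 86.6% |

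With 11.8% in both arms, the rejection rate with EASI added was 4.1% to 5.0%.

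A separate simulation (4,000 trials per row, severity OR 0.355) agrees. At 21.6% v 11.8% it gave 45.9% → 46.5% at OR 0.74, 47.0% → 49.3% at 0.55 and 45.2% → 49.2% at 0.41. With uninformative EASI the two models had 46.3% and 46.1%.

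**The case against.** The strongest reply is that baseline severity is already adjusted for, as the protocol specifies, and that adding EASI is an optional refinement. Much of this stands. The duplicated term does not bias the treatment estimate, and under randomisation a chance imbalance in EASI does not inflate type I error. No validity problem follows.

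A reader might also infer more than the documents support:

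- *That severity is strongly prognostic.* The Phase 2a contrast is suggestive only. Its upper category was severe/very severe, whereas this trial's scale stops at severe, so the groups may not match.
- *That omitting EASI definitely loses power.* Nothing in either document relates baseline EASI to response within an IGA level. The entry threshold of 12 truncates EASI and could weaken it as a predictor.
- *That the change addresses the 45% power.* Even at the strongest setting power reaches 51.6%; 80% at those rates needs 227 per arm.
- *That it is free.* EASI is not in the protocol's primary model, the odds ratio becomes conditional on EASI, and linearity on the logit scale is assumed.
- *That EASI should also go into the stratum models.* With about 34 severe patients per arm (if 34% are severe) and 0/13 placebo responders in that Phase 2a stratum, separation is possible. EASI does not cure it, and no calculation covers those models.

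Finally, the simulations used a Week 8 logistic model and not the planned GEE with unstructured working correlation, so behaviour in the full model is untested.

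**Conclusion.** The point holds in a limited form. For every eligible patient B_IGA carries nothing beyond AD; this follows from the documents alone. A finer baseline severity measure is available, and the SAP's own code uses it elsewhere. Substituting it showed no material power loss when EASI is uninformative. The benefit is about 0 points if EASI is uninformative or weak, +1 to +3 at moderate strength (OR per SD about 0.74 to 0.5) and +4 to +6 if strong (about 0.4 to 0.33). Those gains rest on an assumed EASI effect, normal untruncated EASI, and a Week 8 logistic approximation. This is a worthwhile tidy-up of the primary model. It corrects no bias and does not resolve the trial's low power.

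**What to change.** In SAP 2.2.12.1 replace `B_IGA` by continuous `B_EASI` in the model statement and leave the other terms as they are. Do the same for the endpoint of a 2-point IGA decrease and for the Week 10 models that reuse the code (SAP 2.2.12.2). Keep AD, which preserves the protocol's baseline IGA adjustment. Record EASI as an added covariate relative to protocol 12.9.2, and state that the odds ratio is conditional on severity and EASI, with EASI linear on the logit scale. Align the prose of the secondary EASI model with its code.

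In the separate moderate and severe models, drop AD and B_IGA, which are constant there. EASI is optional in those models.

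Timing: fix this before the interim at n=150, not merely before final unblinding, because SAP 2.2.10 uses that look to judge primary-endpoint futility and to resize the trial.

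Cost: one line of code, matching SAP text and a note against the protocol. No new data.

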2.2.12.2 Secondary Endpoints

The secondary endpoints are:

- Proportion of patients achieving an IGA score of 0 (clear) or 1 (almost clear) and a decrease of at least 2 points in IGA in treated population compared to placebo population from baseline to Week 2, 4, 6 and change from baseline to subject's last treatment visit. These analyses will be

included in the previous analyses for the primary endpoint for Week 8. A separate model will be performed for the change from baseline to week 10, using the same PROC GENMOD code.

- Proportion of patients achieving a decrease of at least 2 points in IGA in treated population compared to placebo population from baseline to Week 2, 4, 6, 8 and change from baseline to subject's last treatment visit. These analyses will be conducted in the same way as the primary endpoint analysis. A separate model will be performed for the change from baseline to week 10 using the same PROC GENMOD code.

- Change from baseline in Eczema Area and Severity Index (EASI) in treated population compared to placebo population at Weeks 2, 4, 6, 8 and subject's last treatment visit. These will be analyzed using PROC MIXED with treatment arm, moderate/severe AD, baseline IGA value, visit, and DS treatment*visit as factors. A separate model will be performed for the change from baseline to week 10, using the same PROC MIXED code.

The change from baseline in EASI will be analyzed for the FAS with SAS PROC MIXED using code similar to the following, with CFB_EASI and B_EASI representing the change from baseline and the baseline EASI, respectively. Method=ml is the maximum likelihood estimate.

```
proc mixed method =ml data= FAS;  
class trt visit subj AD;  
model CFB_EASI= trt visit visit*trt AD B_EASI /CL;  
repeated subject=subj/corr=unstr;  
lsmeans trt*visit / diff CL;  
run;
```

- Change from baseline in Numeric Rating Scale (NRS) for Pruritus in treated population compared to placebo population at Weeks 2, 4, 6, 8 and subject's last treatment visit. These will be analyzed using PROC MIXED with treatment arm, baseline AD severity, baseline NRS score, visit, and DS treatment*visit interaction as factors. A separate model will be done for the change from baseline to Week 10, using the same PROC MIXED code.

As NRS is a daily assessment, the analysis of NRS will be performed using the daily average at each visit. At each visit, the average of the NRS values since the previous visit will be computed. Missing values for any

day will be ignored and the between-visit daily average will be computed using non-missing values only. The baseline value will be the average computed during the screening period. This analysis of change from baseline in NRS will be performed the same as the analysis of change from baseline in EASI, with CFB_NRS and B_NRS representing the change from baseline in NRS and the baseline NRS, respectively.

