2.2.12.3 Exploratory Endpoints

- Time to response by Week 8. A Kaplan-Meier lifetable will be constructed using nominal visits. A Wilcoxon-Gehan test will be used to compare all treatments; p-values will also be computed for each of the three treatment pairs for the primary endpoint using the FAS population. This will be a graph.
- Probability of being in response (PBIR) between Weeks 2 and 8. The PBIR will be computed as a descriptive statistic for the primary endpoint using the FAS population. Each visit will be equally weighted in this analysis. This will be a graph.
- Sustained efficacy between Weeks 8 and 10. This analysis will be endpoint-specific. Binary endpoints will be evaluated using logistic regression (PROC LOGISTIC) controlling for baseline IGA score and baseline AD severity while continuous endpoints will be analyzed using proc GLM controlling for the same factors. A shift table will be created presenting the number and frequencies of subjects in response and the shift from Week 8 to Week 10 for the primary endpoint analysis for both the FAS and PPS populations.
- Change from baseline in the Dermatology Life Quality Index (DLQI) score in treated population compared to placebo population at Week 2, 4, 6, 8 and 10 and from Week 8 to Week 10 and change from baseline to subject's last treatment visit.

DLQI is a set of 10 questions, scored 0=Not at all, 1=A little, 2=A lot, or 3=Very much, or 0=Not relevant, except for Questions 1 and 2 that do not include a response of 'Not Relevant'. Missing responses are assigned '0'. The DLQI total score is calculated by summing the score of each question resulting in a maximum of 30 and a minimum of 0. The higher the score, the more quality of life

is impaired. This scoring will be done by the data management group and provided to CTDS in the SDTM datasets.

Mean DLQI will be computed as the Total DLQI divided by the number of questions with non-missing responses. The scoring instructions for DLQI specify that if 2 or more questions are not answered, then the questionnaire will not be scored; this approach is not taken here with Mean DLQI computed instead. Summary statistics for Total DLQI and Mean DLQI will be presented. The analysis of change from baseline in Mean DLQI will be performed the same as the analysis of change from baseline in EASI, with appropriate changes in the variables for change from baseline and Mean DLQI at baseline.

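### The PROC MIXED code for EASI, reused for NRS, Mean DLQI and Mean POEM, carries a GENMOD REPEATED line, so the intended unstructured covariance across visits is not validly specified and its repair is left open

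*SAP*

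**What the plan says.** SAP 2.2.12.2 introduces the EASI model as illustrative code: "The change from baseline in EASI will be analyzed for the FAS with SAS PROC MIXED using code similar to the following". The lines that matter are:

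- "proc mixed method =ml data= FAS", with the gloss "Method=ml is the maximum likelihood estimate";
- "model CFB_EASI= trt visit visit*trt AD B_EASI /CL";
- "repeated subject=subj/corr=unstr";
- "lsmeans trt*visit / diff CL".

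The REPEATED line matches, character for character, the one in the PROC GENMOD block for the primary endpoint in SAP 2.2.12.1.

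The model is then carried over to other endpoints. For pruritus, "This analysis of change from baseline in NRS will be performed the same as the analysis of change from baseline in EASI". For quality of life (SAP 2.2.12.3), "The analysis of change from baseline in Mean DLQI will be performed the same as the analysis of change from baseline in EASI", and the same section says the same of Mean POEM. The separate Week 10 models for EASI and NRS also reuse the code.

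Protocol 12.9.3 asks for an MMRM for the change-from-baseline endpoints. Treatment-by-visit is to be the repeated effect, and the stated purpose is to account for missing data. Neither the protocol nor the SAP text names a covariance structure for these models. SAP 2.2.6, on missing data, refers only to GENMOD.

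**The concern.** In PROC MIXED, the REPEATED statement takes the repeated effect first, then `SUBJECT=` and `TYPE=` after the slash. `SUBJECT=` before the slash and `CORR=` belong to GENMOD. The printed line therefore gives PROC MIXED neither an ordering of a patient's records nor a covariance type. No prose supplies either, so the only written covariance specification for two secondary and two exploratory endpoints is invalid for its procedure.

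Someone will have to repair it, and the possible repairs are not equivalent. At stake are the standard errors at each visit and the use of a patient's observed scores to inform visits after dropout, which is why the protocol asked for a repeated effect. That choice should be fixed before unblinded data are seen.

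**Working it through.** The documents state no figure on this point, so there is none to reproduce. The check has two parts.

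**1. The possible repairs**

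| Repair of the printed line | Resulting model |
|---|---|
| None | Should stop with an error and give no output |
| Drop the invalid options | Independent residuals, one variance for all visits |
| Add `TYPE=UN`, no visit | Unstructured, but records are placed by order of appearance. If a middle visit is missed and its row is absent, later scores take the wrong matrix position |
| Add visit and `TYPE=UN` | The intended MMRM |

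The second and third rows are alternatives: a single fit cannot have both faults. The third needs intermittent gaps; monotone dropout does not cause it.

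**2. Size under the second row**

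Inputs from the documents: 100 patients per arm (SAP 2.2.9), two-sided 0.05 (SAP 2.2.8), the printed mean model, and four on-treatment visits (Weeks 2, 4, 6, 8).

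Assumed, because the documents give no values: SDs of EASI change by visit, flat (8/8/8/8) or rising (6/7/8/9 or 5/7/9/11); within-patient correlation 0.4 to 0.8; 0% or 20% monotone dropout; 35% of patients severe.

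Simple version, complete data. The model applies one pooled SD to every visit:

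- pooled SD = √(mean of the visit variances)
- ratio of reported to true SE at a visit = pooled SD / SD at that visit
- actual error = 2 × [1 − Φ(1.96 × ratio)]

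For 6/7/8/9: √[(36 + 49 + 64 + 81)/4] = √57.5 = 7.58.

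- Week 8: 7.58/9 = 0.843; error = 2 × [1 − Φ(1.65)] = 9.9%.
- Week 2: 7.58/6 = 1.264; error = 2 × [1 − Φ(2.48)] = 1.3%.

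For 5/7/9/11: √[(25 + 49 + 81 + 121)/4] = √69 = 8.31.

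- Week 8: 8.31/11 = 0.755; error = 2 × [1 − Φ(1.48)] = 13.9%.

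Full version. The printed mean model is fitted by ML with independent residuals, and its SE is compared with the true sampling SE of the same estimate, over all the assumed correlations and both dropout rates:

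| SDs at Weeks 2/4/6/8 | Week 8 reported/true SE | Week 8 actual error | Week 2 reported/true SE |
|---|---|---|---|
| 8/8/8/8 | 0.99 | about 5% | 0.99 |
| 6/7/8/9 | 0.82-0.84 | 10-11% | 1.23-1.25 |
| 5/7/9/11 | 0.73-0.75 | 14-15% | 1.59-1.65 |

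The result is therefore driven by how far variability changes across visits. With flat SDs the Week 8 SE is nearly right, even with 20% dropout.

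A separate cost remains with flat SDs. With 20% dropout, the true Week 8 SE under independence is 1.239 against 1.214 with the correct covariance at correlation 0.4 (1.239/1.214 = 1.02), and 1.286 against 1.182 at exchangeable correlation 0.8 (1.286/1.182 = 1.09). Ignoring within-patient correlation thus loses 2% to 9% of precision.

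**ML against REML.** With about 5 mean parameters per visit, √[(300 − 5)/300] = 0.992, so the SE is 0.8% smaller. Counting the printed model's 12 treatment-by-visit cells plus two covariates over four visits gives 14/4 = 3.5 per visit, and √[(300 − 3.5)/300] = 0.994, or 0.6%. Either way it is under 1%.

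**The case against.** The strongest reply is that this is a copying slip in code offered only as a guide. The line should fail visibly, so no wrong result appears unless someone then repairs it badly. The option `corr=unstr` shows that an unstructured matrix was meant, and Protocol 12.9.3 already calls for a repeated-measures model with visit in the repeated effect. An independence fit would contradict both.

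Most of that stands, and it limits the point to a specification error with an obvious intended reading. It does not remove it. The protocol names no covariance type. The SAP prose is not a safe fallback either: for EASI it lists baseline IGA as a factor, while the code uses baseline EASI.

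Four stronger readings are tempting, and the documents do not support them.

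- *Week 8 results will carry 10-15% error.* This needs both the stated unstructured intent to be ignored and SDs that rise over visits. The documents give no SDs for EASI change, nor for NRS, DLQI or POEM.
- *The primary analysis is compromised.* Its GENMOD line also omits visit, so intermittent gaps can misalign the working correlation. GEE's default empirical standard errors do not need a correct working correlation, so the cost is mainly efficiency.
- *ML is a mistake.* It is an openly stated choice worth under 1% of the SE at 300 patients.
- *The Week 10 models share the fault.* With one record per patient they have no within-patient covariance to specify, although the invalid line still needs correcting there.

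**Conclusion.** The point holds as a correction that should be made. The only written covariance specification for EASI, NRS, Mean DLQI and Mean POEM is invalid in PROC MIXED, names no visit, and does not deliver the MMRM that Protocol 12.9.3 requires.

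The consequence depends on the repair. With visit and an unstructured type supplied, there is no harm. If the invalid options are dropped, Week 8 error ranges from about 5% to 14-15% across the assumed SD patterns, Week 2 intervals are too wide when SDs rise, and within-patient correlation no longer helps with dropout. If a type is added without visit, scores after an absent middle-visit row are misplaced.

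The sizes rest on assumed SDs, correlations and dropout. The statement that the line fails rests on general knowledge of SAS syntax; SAS was not run. The point concerns secondary and exploratory endpoints.

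**What to change.** - In the PROC MIXED code, replace the REPEATED line with `repeated visit / subject=subj type=un;`.
- State in SAP 2.2.12.2 that visit is the repeated effect within patient, with an unstructured covariance and a named fallback structure if the model does not converge. Add that treatment does not change within a patient, so visit alone orders the records; treatment-by-visit stays in the mean model, where the code already has it. This reconciles the code with the wording of Protocol 12.9.3.
- In the GENMOD code of SAP 2.2.12.1, use `repeated subject=subj / within=visit corr=unstr;`.
- Optionally, use REML with Kenward-Roger degrees of freedom (`method=reml`, `ddfm=kr`).

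The cost is a few lines of code and a short paragraph, to be settled before unblinding. Data collection, sample size and trial conduct do not change.
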